3.12 DATA AND SAFETY MONITORING

This trial will be monitored in accordance with the Pfizer's Pharmacovigilance procedures. Adverse events, and SAEs will be reviewed internally as part of ongoing safety surveillance.

Monthly communications with the investigators and applicable site staff will be conducted to discuss study progress, obtain investigator feedback and exchange, and discuss "significant safety events" (i.e., AEs leading to dose reductions, related SAEs, and deaths).

In addition, an external DSMB will monitor the study every 6-12 months until the last patient has received 2 months of therapy, unless there are concerns that require ongoing monitoring.

While glasdegib has demonstrated safety, it has not been previously studied in cGVHD therapy after allogeneic hematopoietic cell transplantation. Current evidence suggests that mortality after initiation of cGVHD therapy may be as high as 20% at 56 days in some high-risk patient groups (Blood and Marrow Transplant Clinical Trial Network Protocol 0801). No interim analysis is planned during this trial, but there will be continuous monitoring for a stopping rule if an exact 1-sided 80% confidence interval for the true non-relapse mortality exceeds 10% -- for example, if 2 of first \leq 8, 3 of first \leq 15, 4 of first \leq 20 experience non-relapse mortality in the first 2 months. If the true probability of non-relapse mortality is 5%, the probability of study suspension under the above rule is approximately 0.08; if the true probability is 40%, the probability of suspension is approximately 0.99, estimated from 5,000 simulations, using R version 3.5.0.

Further details of the stopping rule include the following:

- Treatment-related mortality is any death occurring while receiving study drug, or within 30 days after discontinuation of study drug, that is possibly, probably or definitely related to the drug
- Relapse or progressive disease will factor into the attribution of cause but will not automatically prevent a death from being classified as treatment-related
- For purposes of this stopping rule, the count of patients (8, 15, etc) will reflect the order in which patients start treatment

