- If a DSMB review is required because the stopping rule is triggered, patients who are already enrolled and taking glasdegib may continue treatment, pending the outcome of that review. Any enrolled patient who has consented but not started study drug may not start glasdegib treatment, pending the outcome of that review.
- The DSMB may, after review, recommend to stop the trial or continue it with or without modifications.

We will also include a stopping rule for grade ≥ 3 AEs that are known to be adverse reactions to glasdegib and hedgehog inhibitor pathway class drugs, such as musculoskeletal pain, muscle spasm, QT prolongation, anorexia, nausea, diarrhea, dizziness, elevated creatinine, elevated

transaminases, and tooth problems. If the lower bound of an 80% exact binomial confidence interval is > 20%, operationally given the total sample size 20, if any 2 of the first 4 or fewer subjects or any 3 of the first 7 or fewer subjects or any 4 of the first 11 or fewer subjects or any 5 of the 15 or fewer subjects or 6 of the first 20 or fewer subjects have unacceptable toxicity or Grade 3 or higher severity AEs, then enrollment will be halted while the DSMB reviews the study. If the true probability of Grade 3 or higher AE is 5%, the probability of study suspension under the above rule is approximately 0.02; if the true probability is 40%, the probability of suspension is approximately 0.85 (probabilities estimated from 5,000 simulations, using R version 3.5.0).

Since 2 of the first 4 patients experienced grade 3 muscle cramping, the stopping rule was triggered. Of note, these 2 patients had cramping prior to enrollment. The DSMB reviewed the data and allowed enrollment to continue but with an exclusion criterion for pre-enrollment grade 2 or 3 muscle cramps, or grade 1 cramps that occur at least weekly. For the purposes of the stopping rule, we will start again with subject #5, so if 2 of the next 4 or fewer, 3 of the next 7 or fewer, 4 of the next 10 or fewer, or 5 of the next 15 have unacceptable toxicity or grade 3 or higher severity AEs, then enrollment will be halted again while the DSMB reviews the study. If the true probability of Grade 3 or higher AE is 5%, the probability of study suspension under the above rule is approximately 0.02; if the true probability is 40%, the probability of suspension is approximately 0.85 (probabilities estimated from 5,000 simulations, using R version 3.5.0).

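### Section 3.12: the original grade 3 or higher AE stopping rule suspends with probability 0.92 at a 40% true rate, not the printed 0.85

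*Combined protocol and SAP*

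**What the plan says.** Section 3.12 (Data and Safety Monitoring) sets a stopping rule for grade 3 or higher adverse events known for glasdegib and its class. It is based on an 80% exact binomial limit exceeding 20% and is made concrete "operationally given the total sample size 20". The limits start with "if any 2 of the first 4 or fewer subjects", go on to "any 3 of the first 7 or fewer subjects or any 4 of the first 11 or fewer subjects", then 5 of 15, and end with "6 of the first 20 or fewer subjects have unacceptable toxicity". For this rule the section gives a suspension probability of about 0.02 at a 5% true rate, and "if the true probability is 40%, the probability of suspension is approximately 0.85".

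The next paragraph reports that 2 of the first 4 subjects triggered the rule and that counting restarts at subject #5. The new limits are 2 of 4, 3 of 7, and then "4 of the next 10 or fewer, or 5 of the next 15 have unacceptable toxicity". The same two probabilities follow in the same words, so the sentence with 0.85 occurs twice. The occurrence at issue is the first, which belongs to the original rule. Both sets are described as "probabilities estimated from 5,000 simulations, using R version 3.5.0".

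**The concern.** The two rules are not the same. The original has five limits and runs to 20 subjects. The restarted one has four limits, runs to 15, and has 4 of 10 where the original has 4 of 11. A rule with an extra limit and five more subjects should stop more often at a high event rate, so identical figures at 40% are suspicious.

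This figure tells a safety board how likely the rule is to catch an unacceptable regimen. If it is wrong, the protocol misstates the sensitivity of the rule that monitored the first four subjects. Someone comparing the two paragraphs would also conclude that the restart lost no sensitivity relative to the 20-subject rule.

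**Working it through.** **Inputs (all from section 3.12).** Original limits: 2 of 4, 3 of 7, 4 of 11, 5 of 15, 6 of 20. Restarted limits: 2 of 4, 3 of 7, 4 of 10, 5 of 15. True rates 5% and 40%. Simulation size 5,000.

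**Method.** Let X(n) be the number of the first n subjects with an event. Subjects are independent with event probability p. The rule stops the first time X(n) reaches the limit in force at n. The count never falls and the limit is constant within each block (1–4, 5–7, 8–11, 12–15, 16–20). Checking after every subject is therefore the same as checking at the end of each block. The paths that have not stopped are carried forward block by block with binomial probabilities.

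**Check on a rule whose figures are not in doubt.** The mortality rule in the same section (2 of 8, 3 of 15, 4 of 20) gives 0.0748 at 5% and 0.9909 at 40%. The printed values are 0.08 and, for the latter, "if the true probability is 40%, the probability of suspension is approximately 0.99". The method reproduces them. Without its 4-of-20 limit that rule gives 0.979 at 40%, which would round to 0.98, so the printed mortality figure includes the last limit.

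**Original rule at p = 0.40.**

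| After subject | Not yet stopped, by event count | Cumulative probability of stopping |
|---|---|---|
| 4 | 0: 0.1296; 1: 0.3456 | 1 − 0.4752 = 0.5248 |
| 7 | 0: 0.0280; 1: 0.1306; 2: 0.1866 | 0.6547 |
| 11 | 0: 0.0036; 1: 0.0266; 2: 0.0790; 3: 0.1139 | 0.7768 |
| 15 | 0: 0.0005; 1: 0.0047; 2: 0.0207; 3: 0.0518; 4: 0.0709 | 0.8515 |
| 20 | see below | 0.9167 |

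The first row is 0.6⁴ = 0.1296 and 4 × 0.4 × 0.6³ = 0.3456. In the last block, a subject group with j events at 15 stops if at least 6 − j of the next 5 have events:

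- j = 4: P(at least 2 of 5) = 0.6630; 0.0709 × 0.6630 = 0.0470
- j = 3: P(at least 3 of 5) = 0.3174; 0.0518 × 0.3174 = 0.0164
- j = 2: P(at least 4 of 5) = 0.0870; 0.0207 × 0.0870 = 0.0018
- j = 1: P(5 of 5) = 0.0102; 0.0047 × 0.0102 = 0.00005

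These sum to about 0.065. Added to 0.8515, this gives 0.9167 when intermediate values are not rounded. A simulation of 1,000,000 runs gave 0.9169.

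**Both rules side by side (exact).**

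| True rate | Original, 20 subjects | Restarted, 15 subjects | Printed for both |
|---|---|---|---|
| 5% | 0.016 | 0.016 | 0.02 |
| 10% | 0.073 | 0.068 | – |
| 20% | 0.347 | 0.297 | – |
| 30% | 0.700 | 0.606 | – |
| 40% | **0.917** | 0.845 | 0.85 |

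**A shortcut that needs no recursion.** The original rule stops whenever at least 6 of 20 subjects have an event. P(X ≥ 6 | n = 20, p = 0.4) = 0.874. This already exceeds 0.85, and earlier limits can only add to it.

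**Simulation error.** √(0.917 × 0.083 / 5000) = 0.0039 and √(0.85 × 0.15 / 5000) = 0.0050. The gap is 0.9167 − 0.85 = 0.0667, which is 17 or 13 standard errors.

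**Are the printed limits themselves wrong?** The exact one-sided 80% lower bounds at 2/4, 3/7, 4/11, 5/15 and 6/20 are 0.212, 0.228, 0.217, 0.213 and 0.201. All exceed 0.20, and rebuilding the limits from this criterion returns exactly the printed set. Limits rebuilt from a two-sided 80% interval differ from the printed ones and give 0.828. The limits are sound; the probability attached to them is not.

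**The case against.** The strongest reply is that nothing depends on the number. The original rule has fired and governs no remaining subject, the operative rule's figures are correct, and the error understates the chance of stopping a toxic regimen. All of that stands, and it limits the point to a minor correction.

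A second reply concerns the exact replacement. Crossing the limit halts enrollment, and a first crossing at subject 20 cannot halt enrollment in a 20-subject trial. Counting crossings only through subject 19 gives 0.8985 instead of 0.9167. The mortality rule cannot settle which convention was used, since 0.9880 through subject 19 and 0.9909 through subject 20 both round to 0.99. However, the rule is written for 20 subjects with a limit at 20, and the printed figure is for suspension under that rule, so 0.92 is the natural value. Either convention contradicts 0.85.

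A third reply is that the calculation may have ended at 15 subjects: without the 6-of-20 limit the original rule gives 0.8515. That could explain the figure, as could copying from the restarted rule (0.8452). The documents do not say, and rounding hides the difference. Neither route makes 0.85 correct for the rule as printed.

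**Conclusion.** The figure is wrong as written. For the original rule the suspension probability at a 40% true rate is 0.917, 6.7 points above the printed 0.85. Of this, 6.5 points (0.9167 − 0.8515) come from the 6-of-20 limit. Put the other way, the chance of not suspending is 8.3%, where 0.85 implies 15%. The original rule reaches 0.85 at a true rate of about 36%. The other three adverse-event figures are right: 0.02 for each rule, and 0.85 for the restarted rule.

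This rests on independent subjects with a common event rate, on the limits as printed, and on counting a crossing at subject 20 as a suspension. Severity is minor. It is not a criticism of the decision to restart the count.

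**What to change.** In section 3.12, in the sentence giving operating characteristics for the original 20-subject rule, replace 0.85 with 0.92 and keep 0.02. Leave 0.02 and 0.85 unchanged for the rule restarted at subject #5. If the sponsor wants the two rules to be comparable at a glance, one optional sentence could say that at true rates of 30% and 40% the restarted rule suspends with probability 0.61 and 0.85 over the next 15 subjects, against 0.70 and 0.92 for the original rule applied from the start to 20 subjects.

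The cost is one corrected number. No limit, halt, reporting route or analysis changes.

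### The restarted adverse-event stopping rule lists 4 of 10, while the plan's own confidence-bound criterion and its first list give 4 of 11; the effect is small, but the two lists need reconciling

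*Combined protocol and SAP*

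**What the plan says.** All of this is in section 3.12 (Data and Safety Monitoring).

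- **Criterion:** "If the lower bound of an 80% exact binomial confidence interval is > 20%, operationally given the total sample size 20".
- **Initial list:** "if any 2 of the first 4 or fewer subjects or any 3 of the first 7 or fewer subjects", then "any 4 of the first 11 or fewer subjects", then "any 5 of the 15 or fewer subjects or 6 of the first 20 or fewer subjects".
- **Restart:** two of the first four patients had grade 3 cramping, so the rule was triggered. The DSMB let enrollment continue with an added exclusion criterion, and the plan states: "For the purposes of the stopping rule, we will start again with subject #5".
- **Restarted list:** "if 2 of the next 4 or fewer, 3 of the next 7 or fewer", then "4 of the next 10 or fewer, or 5 of the next 15 have unacceptable toxicity".
- **Stated performance:** the same sentence follows both lists. It gives a suspension probability of about 0.02 at a true event rate of 5% and about 0.85 at 40%, from 5,000 simulations.

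The restart text gives no new confidence level or threshold, and it does not explain the change at four events.

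**The concern.** The restart is described as the same rule beginning again, so the same criterion should give the same limits up to the 16 subjects that remain. At two, three and five events it does. At four events the limit falls from 11 to 10. For a stopping rule, a smaller denominator is the looser limit, because four events must arrive sooner to trigger a halt.

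If the fourth event occurred in the 11th restarted subject (subject 15 overall), the criterion would call for a halt and the list would not. The DSMB would then have two answers from one section, in a rule that has already been triggered once.

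The repeated probability sentence raises a smaller question. A 20-subject rule with a limit at six events and a 16-subject rule without one would not be expected to share the same suspension probability at a 40% rate.

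**Working it through.** **Inputs, all from section 3.12 except N.** Threshold 20%; 80% exact bound; the two lists; stated probabilities 0.02 and 0.85. Total N = 20 (section 3.0), so 20 − 4 = 16 subjects count towards the restarted rule.

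**Step 1. Reproduce the initial list.** The one-sided 80% Clopper-Pearson lower bound for x events in n subjects is the 0.20 quantile of Beta(x, n − x + 1). It exceeds 0.20 exactly when P(X ≥ x | n, p = 0.20) < 0.20. For each x, the limit is the largest n whose bound exceeds 0.20.

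| Events | Largest n that triggers | Bound | Bound at next n |
|---|---|---|---|
| 2 | 4 | 0.212 | 2/5: 0.169 |
| 3 | 7 | 0.228 | 3/8: 0.199 |
| 4 | 11 | 0.217 | 4/12: 0.198 |
| 5 | 15 | 0.213 | 5/16: 0.199 |
| 6 | 20 | 0.201 | beyond the sample size |

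All five entries of the initial list are reproduced.

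**Step 2. Test the restarted entry.** The bound for 4/10 is 0.239 and for 4/11 it is 0.217, so 10 is not the last n that triggers. By the tail form at n = 11, p = 0.20: P(0) + P(1) + P(2) + P(3) = 0.0859 + 0.2362 + 0.2953 + 0.2215 = 0.8389. Hence P(X ≥ 4) = 1 − 0.8389 = 0.161, below 0.20. At n = 12 the tail is 0.205, above it.

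**Step 3. Try the two-sided reading.** With the 0.10 quantile, the limits become 2/2, 3/6, 4/9, 5/13 and 6/16. The bound for 4/10 is then 0.188 and for 2/4 it is 0.143. Neither sidedness gives 10.

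**Step 4. Suspension probability of the restarted rule.** An exact recursion follows 16 subjects with independent events at a constant rate p and checks the rule after each subject. The lists are 2/4, 3/7, 4/10, 5/15 (as written) and 2/4, 3/7, 4/11, 5/15.

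| p | As written | With 4 of 11 | Difference |
|---|---|---|---|
| 5% | 0.0158 | 0.0161 | 0.0002 |
| 10% | 0.068 | 0.070 | 0.002 |
| 20% | 0.297 | 0.306 | 0.009 |
| 30% | 0.606 | 0.617 | 0.011 |
| 40% | 0.845 | 0.851 | 0.006 |

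**Step 5. Account for the difference.** It comes from one path: no earlier halt, the fourth event in restarted subject 11, and no event in subjects 12 to 15. The chance of reaching 4 of 11 this way is 0.0225 at 20%, 0.0447 at 30% and 0.0480 at 40%. Multiplying by (1 − p)⁴ gives 0.0225 × 0.4096 = 0.009, 0.0447 × 0.2401 = 0.011 and 0.0480 × 0.1296 = 0.006, which match Step 4. On the remaining paths through 4 of 11, a fifth event by subject 15 halts enrollment later.

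**Step 6. Check the printed probabilities.** For the restarted rule, both versions round to the stated 0.02 and 0.85. For the initial 20-subject rule, the same recursion gives 0.016 at 5%, which agrees, and 0.917 at 40%, which does not. The simulation standard error there is √(0.917 × 0.083 / 5,000) ≈ 0.004, and the gap is 0.917 − 0.85 = 0.067.

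**The case against.** The confidence-bound sentence introduces the initial list and is tied to 20 subjects. The restarted list followed a DSMB review, does not repeat the bound, and can be read as a self-contained operating rule. On that reading a deliberate 10 cannot be excluded. This part stands: the documents do not prove a slip. But the plan speaks of starting the same rule again, three of the four restarted limits coincide with the criterion, and no reason is given for the fourth. Fewer remaining subjects is not a reason either, because the bound for 4/11 does not depend on how many are still to come.

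It is also fair to say that the consequence is slight. A trigger leads to a DSMB review, not automatic termination, and section 3.12 provides monthly safety communications and external monitoring besides. This limits the importance of the point but leaves the section with two answers at 4 of 11.

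Two stronger readings are tempting. A reader might infer that the restarted rule's stated performance is wrong. It is not: 0.02 and 0.85 hold with either 10 or 11, and for that reason they cannot show which was meant. A reader might also take the gap between 0.917 and 0.85 as a failure of safety protection. The documents do not support that: the initial rule has already been triggered and replaced, and the printed figure understates its chance of suspension.

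The sidedness of the bound is not a defect of substance. The section specifies a one-sided 80% interval for the parallel mortality rule, and all five initial limits match the one-sided form.

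**Conclusion.** The inconsistency is real. The restarted limit of 4 of 10 disagrees with the stated criterion and with the initial list. Exactly one outcome is affected: four events reached at the 11th restarted subject. The cost is at most about 1.1 percentage points of suspension probability at the rates checked (5% to 40%). It deserves correction because it is a decision threshold in a live safety rule, not because the rule performs badly.

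Secondarily, 0.85 at a 40% rate is not a property of the initial 20-subject rule, whose exact value is about 0.92. This corrects a stated figure and changes no future decision.

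The conclusion assumes that the criterion carries over to the restart, that the bound is one-sided, and that the restarted limit of 5 of 15 means 15 or fewer (the qualifier is missing there). The probabilities further assume independent events at a constant rate and a check after every subject.

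**What to change.** Reconcile the two lists in section 3.12. If the criterion is unchanged, it gives 4 of the next 11 or fewer. If 10 was intended, state the criterion that yields it and the reason for the change. Either way, say explicitly which criterion governs the restarted count. Adding that the 80% bound is one-sided would be a useful clarification, but it is optional.

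Give each rule its own probabilities: about 0.02 and 0.92 for the initial 20-subject rule, and about 0.02 and 0.85 for the restarted one.

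The cost is a line or two of protocol text. If the limit becomes 11, the chance of a further DSMB review rises by about one percentage point at most over the rates checked. Sample size and analyses are unaffected.

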5.2 RATIONALE FOR SAMPLE SIZE

With a sample size of 20 patients, the best ORR will be estimated with an 80% exact binomial confidence intervals (CIs).⁴³ If glasdegib is more effective than ibrutinib, the lower bound of the CIs will be used to provide evidence that the true ORR is greater than a specific response rate. For instance, if there are 17 response (CR+PR) out of 20 patients (85%), the corresponding 80% CI will exclude 67% which is greater than the published historical chronic GVHD trials with ORR 67%. However, even if glasdegib is not statistically more effective than ibrutinib, it may still be a preferable treatment if the toxicity is less or the response rate for sclerotic features is encouraging.

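### The restarted adverse-event stopping rule lowers the fourth-event limit from 4 of 11 to 4 of 10 without a reason, and the criterion behind the other limits does not give 10

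*Combined protocol and SAP*

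**What the plan says.** The adverse-event rule in Section 3.12 states its criterion as follows: "If the lower bound of an 80% exact binomial confidence interval is > 20%, operationally given the total sample size 20". It then lists counts, beginning "if any 2 of the first 4 or fewer subjects or any 3 of the first 7 or fewer subjects" and continuing with "any 4 of the first 11 or fewer subjects", 5 of 15 and 6 of 20. Reaching any of these halts enrolment for DSMB review.

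The same section records that 2 of the first 4 patients had grade 3 cramping, which triggered the rule. The DSMB allowed enrolment to continue with an added exclusion criterion, and the count starts afresh with subject 5. The restarted limits are 2 of 4, 3 of 7, and then "4 of the next 10 or fewer, or 5 of the next 15 have unacceptable toxicity". The plan gives suspension probabilities of about 0.02 at a true 5% rate and about 0.85 at 40% for the restarted rule. It restates no confidence level or threshold for these limits and does not comment on the move from 11 to 10.

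The mortality rule in Section 3.12 names its side: "if an exact 1-sided 80% confidence interval for the true non-relapse mortality exceeds 10" per cent. The adverse-event rule does not.

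**The concern.** Three of the four restarted limits are carried over unchanged, and one is not. If the criterion is unchanged, the limit for a given number of events cannot change either: the exact bound for 4 events in 11 patients depends only on 4 and 11, not on how many patients are still to be enrolled. The altered figure is therefore either a slip or an unstated change of criterion.

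This is the boundary in force for the 16 remaining patients, in a trial whose primary objective is safety and tolerability and which has already met the rule once. At the count where the two limits differ, the DSMB would have a criterion that calls for a halt and a printed limit that does not.

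**Working it through.** **Inputs, all from the protocol.** Threshold 20% and 80% exact interval (Section 3.12); original limits 2/4, 3/7, 4/11, 5/15, 6/20; restarted limits 2/4, 3/7, 4/10, 5/15; 20 subjects in total (Section 3.0), so 20 − 4 = 16 after the restart.

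**Step 1: the plan's own figures for the restarted rule.** An exact patient-by-patient recursion, halting at patient n once the event count reaches k with n no greater than the limit for k, gives 0.0158 at a 5% rate and 0.8452 at 40% over 16 patients. These agree with the stated 0.02 and 0.85.

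**Step 2: limits implied by the criterion.** The Clopper-Pearson lower bound for x events in n patients is the a-quantile of a Beta(x, n − x + 1) distribution, with a = 0.20 for a one-sided 80% bound and a = 0.10 for a two-sided 80% interval. For each event count, take the largest n at which the bound exceeds 0.20.

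| Events | One-sided 80% | Two-sided 80% | Original limit | Restarted limit |
|---|---|---|---|---|
| 2 | 4 | 2 | 4 | 4 |
| 3 | 7 | 6 | 7 | 7 |
| 4 | 11 | 9 | 11 | 10 |
| 5 | 15 | 13 | 15 | 15 |
| 6 | 20 | 16 | 20 | none printed |

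The one-sided column reproduces every original limit, and the two-sided column reproduces none. The absence of a sixth-event limit after the restart costs nothing: six events by patient 16 require at least five by patient 15, which already halts.

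**Step 3: the fourth-event limit.**

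- One-sided: 0.2394 at 4/10, 0.2167 at 4/11, 0.1979 at 4/12. The limit is 11.
- Two-sided: 0.2104 at 4/9, 0.1876 at 4/10. The limit is 9.
- Cross-check: with a true rate of 20%, the probability of 4 or more events is 0.1611 in 11 patients, below 0.20, and 0.2054 in 12 patients, above it.

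**Step 4: size.** The rules differ only when the fourth event falls exactly on restarted patient 11. Let S be the probability of exactly 3 events in the first 10 patients with no earlier halt, and p the true rate. The shortfall in halting by patient 11 is S × p. The halt is then lost for good only if patients 12 to 15 have no further event, so the final shortfall is S × p × (1 − p)^4.

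| p | S | S × p | (1 − p)^4 | Final shortfall |
|---|---|---|---|---|
| 5% | 0.0058 | 0.0003 | 0.8145 | 0.0002 |
| 20% | 0.1124 | 0.0225 | 0.4096 | 0.0092 |
| 30% | 0.1490 | 0.0447 | 0.2401 | 0.0107 |
| 40% | 0.1200 | 0.0480 | 0.1296 | 0.0062 |

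The resulting halting probabilities, 4 of 10 against 4 of 11, are:

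| p | By restarted patient 11 | Over all 16 |
|---|---|---|
| 5% | 0.0156 against 0.0159 | 0.0158 against 0.0161 |
| 20% | 0.250 against 0.273 | 0.297 against 0.306 |
| 30% | 0.499 against 0.544 | 0.606 against 0.617 |
| 40% | 0.729 against 0.777 | 0.845 against 0.851 |

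With 4 of 11, the 5% and 40% figures still agree with the stated 0.02 and 0.85, so those figures cannot show which limit was intended.

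**The case against.** The best defence is that the difference hardly matters. Over the remaining enrolment it is about one percentage point at most among the rates examined, a fifth event by patient 15 still halts, the stated operating characteristics are right as printed, and scheduled DSMB reviews and monthly safety discussions go on whatever the count. All of that stands, and it is why the point is minor. It does not explain the figure 10.

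It can also be said that the restart followed a DSMB review and that the criterion is not restated for the new limits, so the change may be deliberate. The documents do not exclude this. They also give no criterion that would produce 10 while leaving the other three limits where they were.

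A reader might infer something stronger from the missing word: that the adverse-event rule is open to a two-sided reading, under which 2 of 4 (lower bound 0.143) would not have triggered. Section 3.12 rules this out. All five printed limits are one-sided, and the section records that 2 of 4 did trigger. Nor does Section 5.2 show that an unlabelled 80% means two-sided in this protocol. Its example of 17 responses in 20 is offered as an illustration, not as a cut-off, and it excludes 67% on both readings (lower bound 0.696 two-sided, 0.741 one-sided). The missing sidedness is an editorial gap that the printed counts resolve.

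**Conclusion.** The restarted fourth-event limit does not follow from the criterion that generates the original limits, and no other criterion is stated. A fourth event at restarted patient 11 meets the one-sided 80% criterion (bound 0.217, above 20%) without halting enrolment under the printed count. The consequence is mainly a later halt: up to about 5 percentage points less chance of stopping by patient 11 at true rates of 30% to 40%, but about 1 point or less over all 16 patients.

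This assumes Clopper-Pearson bounds, independent patients with a common event rate, evaluation after each patient in order, and that the one-sided criterion carries over to the restarted rule. If the sponsor intended a different criterion, the defect is that it is not stated. A reader might conclude that the restarted rule's suspension probabilities are wrong; they are not. Minor severity.

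**What to change.** In Section 3.12, reconcile the restarted fourth-event limit with the original 4 of 11 and the one-sided 80% bound above 20%, or state the different criterion that yields 10 and why it was adopted. As an editorial addition, specify that the 80% interval in the adverse-event rule is 1-sided, as the mortality rule already does.

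Both are wording changes. If reconciliation led to 4 of 11, the probability of suspension would move from 0.0158 to 0.0161 at a 5% true rate and from 0.297 to 0.306 at 20%, and the stated 0.02 and 0.85 for the restarted rule would need no revision.
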